4 STUDY DESIGN

4.1 OVERALL DESIGN

This Study is a Phase 3, multicenter, randomized, double-blind, parallel-group Study designed to evaluate the safety and efficacy of Galnobax® plus SoC versus only SoC, in treating DFU in adults with diabetes mellitus (DM). In addition, Study is designed to evaluate safety of Vehicle plus SoC versus only SoC in Subjects with DFU to investigate deleterious effects of Vehicle on wound healing, if any.

For this purpose, the Subjects will be randomized in 3:3:1 ratio into one of the following groups:

- Group 1: Galnobax® 14% gel plus SoC
- Group 2: SoC only
- Group 3: Vehicle plus SoC

Total number of Subjects in the Study: This Study will have FAS Population (Efficacy Evaluable Population) of a minimum of 240 Subjects in Group 1 and Group 2 (minimum of 120 in each Group). To ensure this and assuming 20% drop out rate, the population of two groups would be maximum of 300 Subjects. In addition, for investigating the effect of vehicle on wound healing, Vehicle plus SoC group will recruit up to 50 Subjects. Thus, overall 350 Subjects will be recruited in the Study.

No. of investigational sites: This Study will be conducted at approximately 40 sites across India with competitive recruitment amongst sites.

Maximum duration of a Subject in the Study: The maximum total duration of Subject in the Study will be 25 weeks spread over three phases in following sequence:

- Screening Phase of 1-week (7 + 3 days)
- Treatment Phase of a maximum of 12-weeks (84±3 days) starting with Baseline visit
- Follow-Up Phase of 12-weeks (84±5 days). This will comprise of Closure Confirmation period of 4 weeks (28±3 days) and Observation period of 8 weeks (56±5 days).

Subject Number Assignment: The Subjects will be assigned randomization number using an interactive web-based randomization system (IWRs). Prior to randomization, Subjects will be stratified by location (plantar or non-plantar) and size ($<5\text{ cm}^2$ or $\geq 5\text{ cm}^2$) of the Target Ulcer solely for the purpose of bringing homogeneity among the three treatment Groups in proportionately. Once a randomization number has been assigned, it cannot be re-assigned to any other Subject.

Application of Treatment: Subjects in the Study will receive treatment twice daily during the 12-weeks of Treatment Phase or up to the Target Ulcer Closure, whichever is earlier. During this period, the twice daily treatment to the Subjects in all the arms of the Study will be administered

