9.2 SAMPLE SIZE DETERMINATION

This Study will have FAS Population (Efficacy Evaluable Population) of minimum of 240 Subjects (minimum of 120 each in Group 1 and Group 2). To ensure this and assuming 20% drop out rate, the population of two groups would be up to 300 Subjects. For safety analysis of Vehicle of Galnobax®, maximum of 50 Subjects will be recruited in Vehicle plus SoC group. Thus, overall population of maximum of 350 Subjects will be recruited in the Study.

Sample Size Determination and Rationale:

The sample size calculation has two components. One is based on statistical power and the other is based on clinical judgment.

The sample size calculation is based on the primary endpoint for the Study that is proportion of Subjects achieving complete closure of Target Ulcer within 12-week Treatment Phase, as determined by blinded Investigator's assessment.

The sample size is obtained based on the assumption that there will be a clinically meaningful difference of 21%, (i.e., 39% of SoC vs 60% of Galnobax®-treated achieved complete closure of Target Ulcer, odds ratio of 0.65). This assumption is based on the following:

- a. Literature reports from various DFU trials showed that average percent wounds closed using SoC treatment is 24% globally.^{5 27} However, percent wounds closed using SoC treatment in recently completed DFU trial in India is reported to be 37.8%.²⁸ In view of this, it is assumed that 39% wounds may close in the SoC group.
- b. In Phase 1/2 study of Galnobax®, 60% wounds closed within 12-week of Galnobax® treatment. Furthermore, 67% wounds were closed in Galnobax® arm for wounds with wound age > 6 weeks. In view of this, the inclusion criterion is revised to include Subjects with wounds of at least 6 weeks (which was 4 weeks in Phase 1/2 study) and it is assumed that 60% wounds may close in the Galnobax® treatment group.

To meet the Type I error rate of 0.05 (95% confidence interval), 2-sided analysis and 90% power, 120 Efficacy Evaluable Subjects in Group 1 and Group 2 will be required for making the FAS Population in the Study as 240. To accommodate the potential drop outs rate of 20%, a total of 300 Subjects will be randomized in these Groups to ensure more than 90% power for the primary endpoint analysis (i.e., proportion of Subjects achieving Target Ulcer Closure within 12-week Treatment Phase).

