The safety evaluation of Vehicle of Galnobax® will be done by recruiting population of 50 Subjects in the Vehicle plus SoC group. As there is not hypothesis testing or statistical comparison proposed for this arm, this population might not be statistically significant, but would enough to give reasonable estimate of safety for Vehicle of Galnobax®.

9.2.1 RANDOMIZATION AND STRATIFICATION OF STUDY POPULATION:

Prior to randomization, Subjects will be stratified by location of Target Ulcer (planter or non-planter), and the Target Ulcer size ($<5\text{ cm}^2$ or $\geq 5\text{ cm}^2$). The randomization will be done at the ratio of 3:3:1 in one of the following groups, using an IWRS:

- Galnobax® 14% plus SoC or
- SoC or
- Vehicle plus SoC

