9.4 STATISTICAL ANALYSES

9.4.1 GENERAL APPROACH

Before database lock, a statistical analysis plan (SAP) will be issued as a separate document, providing the detailed methods for analyses outlined below. Any deviation from the planned analyses will be described and justified in the final integrated clinical Study report.

A maximum of 350 Subjects will be competitively recruited at 40 sites from the DFU Subject population as described in [section 4.1](#).

The number and percentage of all the DFU Subjects entering and completing the clinical Study will be provided across treatment groups. The summarization of primary reason of discontinuation will also be provided across treatment groups.

For this Study, analysis will be done on ITT Population (Safety Evaluable Population), FAS Population (Efficacy Evaluable Population) and PP Population.

The continuous data will be summarized by treatment Group using descriptive statistics (number of Subjects [n], Mean, Standard Deviation [SD], Median, Minimum and Maximum [Range]). Categorical data will be summarized by treatment group using frequency count (n) and percentages (%).

The primary and secondary efficacy analysis will be performed on all Subjects in FAS Population (Efficacy Evaluable Population) and PP Population comparing Group 1 (Galnobax® plus SoC) and Group 2 (SoC only). All the statistical analysis will be performed using SAS® version 9.4 or later.

The Safety analysis will be performed on all Subjects in ITT Population (Safety Evaluable Population).

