9.4.2 ANALYSIS OF THE PRIMARY EFFICACY ENDPOINT

The primary efficacy analysis will be performed on all Subjects in FAS Population (Efficacy Evaluable Population) and PP Population comparing Group 1 (Galnobax® plus SoC) and Group 2 (SoC only) only.

Proportion of Subjects achieving Target Ulcer closure within 12 week Treatment Phase (EOT) = [Number of Subjects having Target Ulcer closed by treatment at or before week 12 (84 ± 3 days)]/[Total Number of Subjects in the Population].

The logistic regression analysis will be used for the primary efficacy analysis for the proportion of Subjects achieving Target Ulcer closure within 12-week Treatment Phase, considering Target Ulcer closed (Yes/No) as dependent variable and treatment group, ulcer type (plantar or non-plantar), and site as independent factors and baseline ulcer size as continuous covariate.

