9.4.3 ANALYSIS OF THE SECONDARY EFFICACY ENDPOINT(S)

The secondary efficacy analysis will be performed on all Subjects in FAS Population (Efficacy Evaluable Population) and PP Population comparing Group 1 (Galnobax® plus SoC) and Group 2 (SoC only) only and are defined as:

- Time to Target Ulcer Closure in days = (Date of Target Ulcer Closure by Week 12 of treatment or earlier – Date of first dose of Study treatment) + 1
- Proportion of Subjects achieving Target Ulcer Closure till End of Study = [Number of Subjects having Target Ulcer Closure at by week 24 or earlier /Total number of Subjects in the Population].

For analysis of secondary endpoint of time to Target Ulcer closure during the 12-week Treatment Phase, Cox proportional hazards model with treatment group, ulcer type (plantar or non-plantar) and site as independent factors and baseline ulcer size as continuous covariate will be used to compare between the treatment groups. In addition, Kaplan-Meier analysis will also be used to depict the median time (days) to Target Ulcer closure for the two treatment groups.

The other categorical secondary endpoints comparing proportion of Target Ulcer using different criteria will be analyzed using chi-square/fishers exact test as well as the same method described for primary efficacy analysis with the same model of logistic regression.

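### The primary logistic model lists site as a factor over about 40 competitively recruiting sites with no rule for sparse sites; fitted as ordinary fixed effects, its type I error is about 5.5–7.5%, not 5%

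*Combined protocol and SAP*

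**What the plan says.** Section 9.4.2 specifies logistic regression of closure (yes/no) on "treatment group, ulcer type (plantar or non-plantar), and site as independent factors and baseline ulcer size as continuous covariate". Site has the same standing in that list as treatment and ulcer type. The text does not say whether it is fixed, random, conditioned on or pooled.

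On the number of sites, section 4.1 says: "This Study will be conducted at approximately 40 sites across India with competitive recruitment amongst sites". Section 9.4.1 says: "A maximum of 350 Subjects will be competitively recruited at 40 sites". The primary comparison uses Groups 1 and 2 only. Section 9.2 sets the error rates ("To meet the Type I error rate of 0.05 (95% confidence interval), 2-sided analysis and 90% power") and the size ("120 Efficacy Evaluable Subjects in Group 1 and Group 2 will be required for making the FAS Population in the Study as 240"), with 300 randomised to these two groups to allow for 20% drop-out.

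Site is not a randomisation stratum. Under section 9.2.1, "Subjects will be stratified by location of Target Ulcer (planter or non-planter), and the Target Ulcer size".

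Section 9.4.3 analyses closure by End of Study with a "chi-square/fishers exact test as well as the same method described for primary efficacy analysis with the same model of logistic regression", and also lists site as a factor in the Cox model for time to closure.

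Section 9.4.1 states that "a statistical analysis plan (SAP) will be issued as a separate document, providing the detailed methods for analyses outlined below". That separate document was not available for this review. No rule for sites with few subjects, or with all or no ulcers closed, appears in the text we have.

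**The concern.** A model with one term per site and only a handful of subjects per site has too many nuisance parameters for ordinary maximum likelihood. The treatment coefficient is pushed away from zero, and its standard error does not widen enough to compensate. Two things follow. When there is no treatment effect, the test rejects too often, in both directions. When there is an effect, the fitted odds ratio is too large.

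This affects the single primary test of a Phase 3 trial. The design does not require the site term, because randomisation is not stratified by site. The same term recurs in both secondary models.

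**Working it through.** **1. The plan's own sample size.** Inputs from section 9.2: 39% vs 60%, two-sided 0.05, 90% power. With pooled variance (mean proportion 0.495):

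n = [1.960·√(2·0.495·0.505) + 1.282·√(0.39·0.61 + 0.60·0.40)]² / 0.21² = (1.386 + 0.886)² / 0.0441 ≈ 117.0, so 118 per group.

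The plan's 120 gives 90.7% power, and 240/0.80 = 300. Both figures reproduce.

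**2. How thin the data are.** 240/40 = 6 and 300/40 = 7.5 subjects per site. With all 40 sites active the model has 1 + 1 + 1 + 1 + 39 = 43 parameters (intercept, treatment, location, size, sites). At 49.5% closure, 240 subjects yield about 119 closures, or 119/43 ≈ 2.8 per parameter. With uneven recruitment of 240 subjects, about 34 of 40 sites recruit anyone. About 16 of these have fewer than 5 subjects. About 9, holding 18 subjects, are all closed or all open and give no information on treatment.

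**3. Type I error.** Groups 1 and 2 were simulated 1:1 under no treatment effect, with 12,000 trials per scenario (Monte Carlo SE about 0.2 points). The documents give no figures for the following, so they are assumptions:
- permuted blocks of 6 within the four location-by-size strata
- 60% plantar
- log-normal ulcer size (median 4.5 cm², log SD 0.5) clipped to 2–15 cm²
- log-odds effects of −0.4 for location and −0.10 per cm²
- site SD 0.5 on the logit scale
- site sizes equal, exponential (uneven) or gamma with shape 0.3 (strong skew)
- null closure 49.5%

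The fitted model had treatment, location, continuous size and site indicators, with a Wald test.

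| Subjects, sites, recruitment | Fixed site terms | No site term |
|---|---|---|
| 240, 40, uneven | 6.4% | 4.9% |
| 240, 40, equal | 7.0% (7.7% in a further 4,000 trials) | 4.8% (5.1%) |
| 240, 40, strong skew | 5.7% | 5.1% |
| 240, 25, uneven | 5.7% | 4.8% |
| 240, 20, uneven | 5.7% | 5.1% |
| 300, 40, uneven | 6.4% | 5.0% |
| 300, 40, equal | 6.9% | 5.1% |
| 300, 40, strong skew | 5.9% | 5.3% |
| 300, 20, uneven | 5.8% | 5.3% |

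By tail (240, uneven): 3.15% favouring Galnobax and 3.22% favouring SoC, against 2.5% each. The mean log-odds ratio under the null is 0.00 throughout.

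A second set of simulations (20,000 trials per scenario; base closure 39% or 50%; site SD 0, 0.5 or 1.0; 20, 27 or 40 sites) gave 5.6–7.5% by Wald test and 5.8–7.8% by likelihood-ratio test, against 4.7–5.2% without site. With no true site differences the Wald figure was still 6.7%, so the cause is the number of site parameters rather than the assumed site variation.

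**4. Exaggeration of a true effect.** Calibrating to marginal 39% vs 60% gives a site-specific log-odds ratio of 0.922 (OR 2.51). Mean estimates with fixed site terms:
- 240 uneven: 1.076. Ratio 1.076/0.922 = 1.17, and OR e^1.076 = 2.93.
- 240 equal: 1.151, or 25% too large.
- 240 with strong skew, 25 sites or 20 sites: 1.012–1.017, or 10%.
- 300, all patterns: 0.997–1.092, or 8–18%.

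**5. Alternatives, 240 subjects and 40 sites** (2,000–4,000 trials each).

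| Handling of site | Type I error | Power |
|---|---|---|
| Random intercept, 15-point quadrature | 4.5–5.2% | 91–93% |
| Omitted | 4.7–5.1% | 91–92% |
| Conditional logistic by site | 4.2–5.0% | 86–88% at site SD 0.5; 93% at SD 1.0 |

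Pooling sites into six regions as fixed effects, in the second set, gave 5.0–5.5% type I error.

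**6. Cox model, 240 subjects.** Assumed: weekly observed closure, Efron ties, site SD 0.3, log-hazard effects of −0.25 for location and −0.07 per cm². Hazard ratio = ln(0.40)/ln(0.61) = 1.85 (log 0.617). Fixed site terms gave 7.3% (uneven) and 8.4% (equal) type I error, against 5.1–5.2% without site. The log-hazard ratio was 0.688 and 0.716, or 11–16% too large. Stratifying by site gave 4.8–5.1%, with power 83–85% against 90% without site.

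**7. A label in section 9.2.** 0.39/0.60 = 0.65 is a risk ratio. The odds ratio is (0.39/0.61)/(0.60/0.40) = 0.426.

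**The case against.** The strongest reply is that 9.4.2 is only an outline and the handling of site is the kind of detail a separate SAP settles. That document may contain a rule, so what is established is a gap in this text and the consequence of its natural reading. But the SAP is meant to detail the analyses outlined here, and the outline already contains site as a factor. Settling the estimator after site sizes and convergence are known would add avoidable discretion to the primary test.

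Other points stand in part:
- **Size.** Figures of about 7% or more arise mainly with equal recruitment, which the protocol does not expect. With uneven recruitment the range is about 5.6–6.9%, and with 300 subjects on skewed or few sites the site terms add only about 0.5–0.6 points. The effect is modest.
- **Effect measure.** Section 9.4.2 names no odds ratio for reporting. The exaggeration matters only if one is taken from this model; the observed closure proportions are unaffected.
- **Cox ties.** Section 9.4.3 does not name the method. A smaller run with Breslow ties (1,000 null trials, uneven) gave about 6.2% type I error and 7% exaggeration, so the Cox figures above are specific to Efron.
- **Choice of remedy.** Several options hold about 5%, and choosing among them is partly preference.

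**Conclusion.** The concern holds. Read naturally, the primary model misses the 5% in section 9.2 by roughly 0.5 to 2.5 points and overstates a true log-odds ratio by 8–25%. The most relevant case, 240 subjects at 40 uneven sites, gives 6.4% and 17%. The direction was the same under every recruitment pattern and base rate tried. The exact size rests on assumed site sizes and covariate effects, and on site being fitted by ordinary maximum likelihood, which the plan implies but does not state. This should be fixed before database lock. It does not call the sample size into question. The odds-ratio label is a clerical correction and carries no weight here.

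**What to change.** State in 9.4.2 how site enters the model. Either fit it as a random intercept, naming the estimation method (the figures above used 15-point quadrature), or omit it. Keep treatment, ulcer location and baseline ulcer size in both cases. Apply the same choice to the logistic model reused in 9.4.3. In the Cox model, omit site, or stratify by it, instead of fitting one term per site. In 9.2, relabel 0.65 as a risk ratio and give the odds ratio as 0.43.

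The cost is one line in 9.4.2, one in 9.4.3 and one label. With a random intercept or site omitted, sample size and conduct do not change. Omitting site leaves between-site differences unadjusted and gives an odds ratio averaged over sites: log-odds ratio 0.89, against a site-specific 0.92 at site SD 0.5 or 1.05 at SD 1.0. Conditional logistic regression by site is also valid but costs about 3–5 points of power at 240 subjects when sites differ little, so the 90% in 9.2 would need restating. Stratifying the Cox model costs about 5–7 points.

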Additionally, the non-clinical PK studies evidence that by application of Galnobax®, Esmolol hydrochloride is minimally absorbed (less than 10 ng/mL in rats and average maximum concentration of 30 ng/mL in minipigs) into systemic circulation, thereby evidencing that Galnobax® is safe to use in the treatment of DFU. The above observations and the fact that Esmolol hydrochloride is a pharmaceutically approved drug with well elucidated safety profile, suggest that Galnobax® has significantly favorable risk/benefit profile.²¹

Clinical Studies

The efficacy analysis of Phase 1/2 clinical Study of Galnobax® numerically establishes that Galnobax® 14% treatment has advantage in terms of area and volume reduction over the Vehicle and Galnobax® 20%. This advantage of Galnobax® 14% is more pronounced in hard to heal DFU:

- **In plantar DFU:** Galnobax® 14% showed 98.1% area closure Vs 75.8% for Placebo. The median time for complete wound closure was 35 days for Galnobax® 14% Vs 64 days for Placebo²¹
- **In older DFU:** On DFUs older than 8 weeks at baseline, Galnobax® 14% group showed complete closure in 75% Subjects Vs 43% in Placebo group²¹

The safety analysis of Phase 1/2 clinical Study establishes and reconfirms the findings of the non-clinical studies that Galnobax® is safe for long term use (tested for 12-weeks) in both 14% and 20% concentrations. Overall 29 adverse events (AEs) were observed in the Study and only two were related to the Study treatment. These two AEs were local mild allergic reactions which were found to be reversible. The safety of Galnobax® is further reinforced by the pharmacokinetic analysis of Phase 1/2 clinical Study which establishes that the systemic concentration of its drug substance (Esmolol hydrochloride) was below quantification limit (10 ng/mL) at any time during the

treatment period, irrespective of wounds of different sizes and doses of Galnobax®. This observation is significantly lower than:

- Systemic concentration of 868-1470 ng/mL observed for approved doses of intravenous Esmolol hydrochloride
- Human peak plasma concentration of 500, 1200 and 2500 ng/mL respectively observed for the infusion of Esmolol hydrochloride at the rate of 100, 250 and 500 µg/kg/min²²

Considering the above facts, it is proposed to investigate Galnobax® 14% in a Phase 3 Study to establish safety and efficacy with statistical significance.

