8 STUDY ASSESSMENTS AND PROCEDURES

Screening Visit V1 (Day -10 to Day -7)

The Screening Phase is designed to determine whether Subjects are eligible to proceed to the Treatment Phase of the Study. The activities in this Phase include:

- Obtain written consent from the Subject/LAR
- Investigator or authorized Study staff will explain to the Subject/LAR, the Study procedures and signed informed consent will be obtained

Note: Signed informed consent must be obtained prior to Subject participation in any protocol-related activities that are not part of routine care.

The following assessments and procedures will be performed and results will be recorded:

- Inclusion-exclusion criteria evaluation
- Demographic information of the Subject
- Sample collection for Urine pregnancy test (as necessary)
- Initial evaluation including medical history and foot specific history. The ulcer history will include the location and duration of all the potential Target Ulcers. In addition to disease history [DM (Type 1 or Type 2)], all other medical and social histories, in the opinion of the Investigator, that are relevant to the safety of the Subject or could impact safety or efficacy results for the Subject will be recorded. Recording of all current and prior treatment/therapies used within the 30 days prior to the V1 visit
- Vital signs (blood pressure, pulse rate, respiratory rate, and temperature)
- Systematic physical examination and body weight
- Laboratory tests (hematology tests, biochemistry, and HbA1c)
- ECG or 2 D echocardiography (2D-ECHO only if ECG is not conclusive)
- Ankle-Brachial Index assessment and corresponding eligibility assessments as per Inclusion Criteria for ABI (See Attachment 2).
- Assessment of Study foot by SW 5.07 monofilament test. Peripheral neuropathy will be assessed by using a 10-g Semmes Weinstein 5.07-gauge monofilament to test 4 points on

the foot for touch sensation (Greater toe, 1st, 3rd and 5th metatarsal head) (See Attachment 3)

- Assessment of all potential Target Ulcers for osteomyelitis. The osteomyelitis should be ruled out by clinical examination and X-ray findings. If the Investigator is unable to ascertain the condition of osteomyelitis by probing of the Target Ulcer or by digital X-ray then Investigator may use other techniques such as MRI, bone scintigraphy, leukocyte scanning or bone biopsy to rule out the presence of osteomyelitis based on availability of the investigation facility

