9.4.11 SUB-GROUP ANALYSES

The subgroup analysis for ulcer type (plantar and non-plantar) and ulcer size ($<5 \text{ cm}^2$ vs. $\geq 5 \text{ cm}^2$) will also be performed for the primary efficacy endpoint i.e. proportion of Subject achieving Target Ulcer Closure within 12-week Treatment Phase by considering ulcer type (plantar and non-plantar) and ulcer size ($<5 \text{ cm}^2$ vs. $\geq 5 \text{ cm}^2$) as the subgroup strata.

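### Ulcer duration, which the protocol treats as related to closure and records at Screening, is left out of the efficacy models and the subgroup analysis

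*Combined protocol and SAP*

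**What the plan says.** Three parts of the protocol tie ulcer age to closure.

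- Section 2.2 says the advantage of the 14% gel is larger in hard-to-heal ulcers. It gives two examples, plantar ulcers and older ulcers. For the latter: "On DFUs older than 8 weeks at baseline, Galnobax® 14% group showed complete closure in 75% Subjects Vs 43% in Placebo group".
- Section 2.3.2 repeats 75% against 43% as a known potential benefit.
- Section 9.2 cites 60% closure on Galnobax overall, adds that "67% wounds were closed in Galnobax® arm for wounds with wound age > 6 weeks", and on that basis raises the minimum ulcer age from 4 weeks to 6.

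Inclusion criterion 5(f) in section 5.1 requires the ulcer to have been open for at least 6 weeks at Screening and sets no upper limit. Duration is collected then: "The ulcer history will include the location and duration of all the potential Target Ulcers" (section 8; also footnote a of the schedule in 1.3).

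The analysis does not use it. Randomisation is stratified by location and size (4.1, 9.2.1). The primary logistic model has "treatment group, ulcer type (plantar or non-plantar), and site as independent factors and baseline ulcer size as continuous covariate". Section 9.4.3 gives the Cox model the same terms and reuses the logistic model for closure by End of Study. Section 9.4.11 reads "The subgroup analysis for ulcer type (plantar and non-plantar) and ulcer size" and names no further factor. Exploratory analyses are marked not applicable (9.4.13).

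**The concern.** Section 2.2 singles out two features, plantar location and age. Location is a stratification factor, a model term and a subgroup. Age is none of these, and no reason is given.

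With no upper limit, ulcers from 6 weeks to possibly years old are pooled. If duration predicts closure, leaving it out costs some precision. If the arms differ in age by chance, no planned analysis allows for it. Any look at the effect by age would then be chosen after the results are known, on a feature for which the sponsor already claims a benefit.

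**Working it through.** **1. The plan's own figure.** Inputs from 9.2: "39% of SoC vs 60% of Galnobax®-treated achieved complete closure of Target Ulcer", two-sided 0.05, 90% power. Section 4.1 gives 3:3:1, which is 1:1 for the efficacy comparison. With pooled variance and no continuity correction:

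n = [1.960·√(2·0.495·0.505) + 1.282·√(0.39·0.61 + 0.60·0.40)]² / 0.21² = 118 per arm.

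The stated 120 reproduces, with power of 90.7% at 120 per arm, and 240/0.8 = 300. Nothing below changes these numbers.

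**2. Chance imbalance.** The documents do not give the distribution of duration. Assume half the ulcers count as older. At 120 per arm, the standard error of the difference in that share is √(2·0.25/120) = 0.0645. The probability of a difference of 10 points or more is 2·[1 − Φ(0.10/0.0645)] = 0.12.

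**3. Power with and without duration.** The documents give neither the strength nor the direction of the association, so each row is an assumption. Simulated trials had 120 per arm and marginal closure of 39% and 60%. The covariate was standard normal, standing for log duration, and the model had no other covariates and no site term.

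| Assumed slope (log odds per SD) | Power without | Power with |
|---|---|---|
| −0.3 in both arms (OR 0.74) | 0.902 | 0.911 |
| −0.5 in both arms (OR 0.61) | 0.908 | 0.925 |
| −0.7 in both arms (OR 0.50) | 0.900 | 0.934 |
| −1.0 in both arms (OR 0.37) | 0.896 | 0.946 |
| −0.3 control, +0.3 drug | 0.899 | 0.903 |
| 0 control, +0.3 drug | 0.908 | 0.910 |

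The first four rows used 3,000 trials each; a second run of those scenarios also gave gains of about 1 to 5 points. The last two rows used 1,500 trials each. The gain is therefore 1 to 5 points with a common negative slope and under half a point when the slopes differ by arm.

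**4. Would a split at 8 weeks work?** An ulcer must be at least 6 weeks old at Screening, and Baseline follows 7 to 10 days later. Every Target Ulcer is therefore at least 42 + 7 = 49 days old at Baseline, and a cut at 8 weeks (56 days) leaves about one week of age below it. The note to criterion 5 in section 5.1 also prefers the older of several qualifying ulcers. If the lower level held 5%, 10% or 20% of 120 per arm (assumed; m = 6, 12 or 24), the 95% half-width for the difference would be 1.96·√[(0.39·0.61 + 0.60·0.40)/m] = 55, 39 or 28 points.

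**5. How much can a balanced split show?** Take 60 per arm on each side.

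- Let the older half close at the Phase 1/2 rates of 43% and 75%, with the younger half at 35% and 45% so that the overall rates stay at 39% and 60%. The difference in log odds ratios is 0.962 with standard error 0.545. Interaction power is Φ(0.962/0.545 − 1.96) = 42%.
- The interaction detectable with 80% power is a ratio of odds ratios of exp[(1.96 + 0.842)·√(2·(1/(60·0.39·0.61) + 1/(60·0.60·0.40)))] = 4.4.

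Such an analysis gives estimates, not a test.

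**The case against.** The case for leaving the plan alone is that randomisation already protects the comparison and that the planned model contains location and size, the stratification factors. The choice of further covariates is partly preference. The Phase 1/2 evidence is thin: 44 subjects in all (2.3.1), with no subgroup counts given. A separate SAP is still to come before database lock (9.4.1). Most of this stands. However, 9.4.1 says the SAP will detail the analyses outlined in the protocol, and duration is not among them. Weak evidence for a feature that shaped the entry criterion is also no reason to leave it out of the analysis.

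Four stronger readings are tempting, and the documents do not support them.

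- *The omission biases the primary result.* It does not; the loss is precision and protection against chance imbalance.
- *The premise for raising the entry limit goes untested because duration is not analysed.* Ulcers under 6 weeks are excluded, so no analysis of this trial can test the change from 4 to 6 weeks.
- *Phase 1/2 showed that age is what separates drug from control.* The 60% and 67% figures are for Galnobax only. Just one cited comparison by age, 75% against 43%, has a control rate, and section 2.2 names plantar location as well. The sample size uses the overall 60%, not 67%.
- *Adding duration buys up to 5 points of power.* That assumes closure falls with age equally in both arms, whereas the cited Galnobax figures rise (60%, 67%, 75%). It also compares against a model with no covariates, while the planned model already has size, ulcer type and site.

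**Conclusion.** The point holds as a modest, low-cost improvement. The protocol treats ulcer age as related to closure, collects duration at Screening, and then uses it in no efficacy analysis. The primary comparison remains valid and the sample size is unaffected.

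The imbalance figure of about 12% rests on the assumed half share of older ulcers. The power gain over the plan as written is not established. What can be said firmly is that a baseline variable the sponsor considers relevant is available, is not adjusted for, and has no pre-specified description of how the effect varies with it.

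**What to change.** - **9.4.2 and 9.4.3:** add log-transformed Target Ulcer duration, as recorded at Screening, as a continuous covariate in the logistic and Cox models. The End-of-Study logistic model follows, since it reuses the primary one.
- **9.4.11:** add a descriptive estimate of how the treatment effect varies with continuous log duration, or by a split at the pooled median chosen while still blinded. Give confidence intervals and label it as low-powered. Do not split at 8 weeks, because the lower level would be nearly empty.
- **Interpretation:** state that the change in the entry limit from 4 to 6 weeks cannot be tested in this trial.

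The cost is one covariate and one table, with matching wording in the protocol and in the SAP due before database lock. No added enrolment or data collection is needed. The downside is small: duration comes partly from patient history and is imprecise, so adjustment will recover only part of any gain.
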